COMIRB Protocol

COLORADO MULTIPLE INSTITUTIONAL REVIEW BOARD
[name] [contact] [contact]

Protocol #: 18-1722

Project Title: **Histologic Comparison of Healing After Tooth Extraction with Ridge Preservation Using Two Different Xenografts**

Principal Investigator: [name]

Version Date: 9.15.21

I. Hypotheses and Specific Aims:

- 1) There will be additional vital bone at 16-20 weeks with Salvin-Oss®.
- 2) To compare the clinical and histological outcome of using Bio-Oss® or Salvin-Oss® in a tooth extraction ridge preservation model.

II. Background and Significance:

Dental implants have become a predictable and reliable therapy in the replacement of missing teeth. ⁽¹⁻³⁾ Extraction sites that are not grafted for ridge preservation may lose up to 50% of their ridge width the first year after extraction. ⁽⁴⁻⁶⁾ Ridge preservation is a simple procedure that has proven to decrease the loss of ridge width during healing. ⁽⁷⁻⁹⁾ Multiple graft products are on the market, such as allografts, xenografts, and alloplasts. All have been used in ridge preservation techniques in an attempt to maintain the ridge width after the tooth was extracted. For this study we focus on xenografts to preserve alveolar bone after tooth extraction prior to placement of a dental implant.

Xenografts are commonly used materials for bone growth and bone contour augmentation techniques. Xenografts have been shown to have osteoconductive potential, ⁽¹⁰⁾ similar to that of the allografts ⁽¹¹⁾, in addition to providing a scaffold for space maintenance. ⁽¹²⁾ The turnover of the xenograft particles has been shown to be longer than that of allografts⁽¹³⁾ which may be beneficial in maintaining the volume of tissue in the area. Prior studies have compared demineralized freeze-dried bone allograft (DFDBA) and freeze-dried bone allograft (FDBA) for

percentage of vital bone⁽¹⁴⁾, however currently there is no study comparing the two most common used xenografts on the market, Bio-Oss® and Salvin-Oss®. The use of xenografts is routine care, and the selection of the specific product is currently based on the cost to obtain the material and provider preference (e.g. personal handling preference). The purpose of the current study is to compare Bio-Oss® and Salvin-Oss® in the preservation of alveolar bone after extraction of non-molar teeth. Bio-Oss® is a bovine product while Salvin-Oss® is porcine. Both products that have similar manufacturer stated outcomes. Bio-Oss® has been on the market longer than Salvin-Oss® and is more costly. Both are FDA approved for bone grafting techniques in humans.

The primary objective is to histologically evaluate and compare the percentage of new bone formation in healing extraction sockets of non-molar teeth grafted with Bio-Oss® versus Salvin-Oss®.

The secondary aim is to observe clinical changes in ridge height and ridge width after grafting with these two materials.

III. Preliminary Studies/Progress Report: none

IV. Research Methods

This is a single site, open label, randomized study, comparing two FDA-approved xenografts, Bio-Oss® and Salvin-Oss®.

A. Outcome Measure(s):

- 1) Histologically measure % vital bone, % residual graft, % of connective tissue**
- 2) Clinically measure:**
 - a. the change of ridge height on the buccal and lingual**
 - b. change of ridge width**
 - c. % change of ridge width**

B. Description of Population to be Enrolled:

40 patients, who must be active, non-emergency patients at the University of Colorado School of Dental Medicine Graduate Periodontics Department will be enrolled in this study. Subjects will be included if they are at least 18 years of age, consent to be in the study, planned for non-emergent dental treatment, and ASA Class I or II.

Patients who qualify must require extraction of a single-rooted non-molar tooth and are interested in receiving a dental implant at the site of tooth extraction. Patients must be committed to have the dental implant placed 16-20 weeks after extraction and ridge preservation

Inclusion criteria: 1) adequate restorative space for implant-retained restoration; 2) ≥ 10 mm alveolar bone height without impingement on the maxillary sinus or inferior alveolar canal; 3) root location and angulation that would be consistent with the subsequent implant placement. To ensure an adequate depth of socket for harvesting a bone core biopsy without inclusion of native bone all roots should have a minimum of 10mm of radiographic bone support, and have angulation similar to the angulation of the implant to be placed at the site.

Subjects will be excluded if <18 years old, currently pregnant or require antibiotic prophylaxis prior to dental procedures as outlined by the 2017 American Heart Association guidelines, decisional challenged adults, are a current smoker or ASA Class III or IV.

Study Design and Research Methods

Patients will be randomly assigned (1:1) to one of two treatment groups (Bio-Oss® or Salvin-Oss®) at the time of surgery through random selection of sealed envelopes.

The xenograft materials to be studied, Bio-Oss® and Salvin-Oss®, will each be obtained from a single batch. This request for single batch materials will be given to the manufacturer prior to shipment of the bone material.

All bone material will be ground to a particle size ranging from 250-1000um per the manufacturer.

3) Measuring of clinical endpoints (as described below):

- a.** the change of ridge height on the buccal and lingual
- b.** change of ridge width
- c.** % change of ridge width

Surgical procedure (Routine Care, except where indicated as research only):

The identified tooth will be extracted per standard of care in a minimally traumatic manner with either no flap or minimal flap reflection no more than 2mm beyond the alveolar crest, followed by curettage and irrigation of the socket. The socket will be thoroughly examined for defects, such as dehiscences or fenestrations. As previously described by Beck and Mealey⁽¹⁵⁾ a University of North Carolina (UNC) periodontal probe will be used to make the following clinical measurements: the height of the buccal and lingual crest will be measured by using a UNC periodontal probe to connect the midfacial cemento-enamel junctions of the adjacent teeth, and then the vertical distance from that reference line to the crest of bone on the midfacial and midlingual will be measured. Calipers will be used to measure the ridge width as well as buccal plate thickness 2mm from the crest of the ridge at the midfacial aspect to the nearest 0.5mm. All measurements will be performed by one of two examiners that will be calibrated. All surgeries will be performed by periodontal residents under the direct supervision of board-certified attending faculty. The faculty will then select the xenograft product to be used based on the

product identified in the sealed envelope. While the measurements are being completed, the randomly selected graft material (Bio-Oss® or Salvin-Oss®) will be hydrated with sterile water. The socket will be filled to or slightly coronal to the crest of the bone. A resorbable collagen membrane material will be placed over the graft material and will be secured over the socket orifice with non-resorbable sutures (this is the standard of care for site preservation techniques). Flaps will not be reflected unless a minor dehiscence is detected. In cases in which there is a bony dehiscence, small flaps will be reflected just beyond the extend of the dehiscence and a collagen membrane material will be used to cover dehiscence (per standard of care). Only minor dehiscences will be accepted; if the depth of the dehiscence is 50% or greater the depth of the socket, the participant will be excluded from the study. Post-operative instructions will be given to the patient along with post-operative analgesics and antibiotics. Sutures will be removed 2 weeks after ridge preservation procedure (per standard of care).

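### Allocation by random pick of sealed envelopes, with no numbering or fixed order described, neither prevents nor reveals a second draw or the reuse of an opened envelope

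*Combined protocol and SAP*

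**What the plan says.** Section IV, under Study Design and Research Methods, gives the allocation method in one sentence on envelopes, quoted here without its last word: "Patients will be randomly assigned (1:1) to one of two treatment groups (Bio-Oss® or Salvin-Oss®) at the time of surgery through random selection of sealed". It does not say who picks the envelope.

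The Surgical procedure text adds how the result is used. After describing extraction, examination of the socket for defects and the clinical measurements, it continues with "The faculty will then select the xenograft product to be used based on the" and closes that sentence with "product identified in the sealed envelope". The next sentence reads "While the measurements are being completed, the randomly selected graft material (Bio-Oss® or Salvin-Oss®) will be hydrated with sterile water". Further on, for dehiscences, it says "if the depth of the dehiscence is 50% or greater the depth of the socket, the participant will be excluded from the study".

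Three other statements bear on the point. The opening of section IV calls the trial single-site and open label. Section IV.B sets enrolment at 40. Section II says of routine care that "the selection of the specific product is currently based on the cost to obtain the material and provider preference (e.g. personal handling preference".

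Nothing in the document describes how a list is generated, whether envelopes are numbered or opaque, the order in which they are used, who prepares and holds them, a log linking envelope to patient, or what becomes of an opened envelope when its patient is excluded.

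**The concern.** Sealing hides the product until the envelope is opened. It does not record which envelope was opened for whom. With numbered envelopes used in order, a discarded or repeated opening leaves a gap or a mismatch that a monitor can find. With a random pick from unnumbered envelopes there is no sequence to check, and nothing shows which product a given patient was due.

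The setting makes this more than a formality. Those who act on the envelope supervise the surgery, the products are not masked, providers are acknowledged to have product preferences, and patients can be excluded during the operation. If a second draw were ever prompted by the look of the socket, harder sites would collect in one arm. The Data Analysis Plan (section IV.E) compares arms with unadjusted t tests, confirmed by Mann-Whitney tests, so the analysis would not correct for that.

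**Working it through.** The plan states no figure on this point, so there is none to reproduce. The check is a reading of the text followed by illustrations on assumed rates.

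**1. What the text controls.** The methods sentence makes the pick itself the random act: "at the time of surgery through random selection of sealed envelopes". The surgical text ties the faculty to whatever the envelope names. Between these two statements no step links an envelope to a patient before it is opened, and none accounts for it afterwards.

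**2. Order of events.** There are two readings, and the text does not decide between them.
- The envelope is opened after the socket examination. Socket condition is then known at the draw, but a patient with a disqualifying dehiscence can be excluded before any envelope is opened.
- The envelope is opened earlier. The draw is then less open to influence from the socket, but a patient may be excluded after opening, and the fate of that envelope is undefined.

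The word *then* before the faculty's selection favours the first reading. Hydrating the graft while measurements are still being made shows that the product is known before the measurements are complete.

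**3. Possible bias in % vital bone.** All inputs are assumptions: a share f = 10-30% of sockets is poor; poor sockets have 10 points less vital bone; one product, when drawn for a poor socket, is rejected and redrawn once with probability r = 50-100%; each draw is an independent 50:50 pick.

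Chance that a poor socket ends with the avoided product: p = 0.5(1 - r) + 0.25r.
Poor share in the avoided product's arm: a = fp / [fp + 0.5(1 - f)].
Poor share in the other arm: b = f(1 - p) / [f(1 - p) + 0.5(1 - f)].
Bias = (b - a) × 10 points.

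| f | r | p | a | b | b - a | Bias (points) |
|---|---|---|---|---|---|---|
| 0.1 | 0.5 | 0.375 | 0.0375/0.4875 = 7.7% | 0.0625/0.5125 = 12.2% | 4.5 | 0.45 |
| 0.2 | 1 | 0.25 | 0.05/0.45 = 11.1% | 0.15/0.55 = 27.3% | 16.2 | 1.62 |
| 0.3 | 1 | 0.25 | 0.075/0.425 = 17.6% | 0.225/0.575 = 39.1% | 21.5 | 2.15 |

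With r = 0, p = 0.5 and a = b = f, so the bias is zero. Otherwise the avoided product looks better than it is.

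**4. Bias against sampling error.** A 30% dropout (section IV.D) leaves 40 × 0.7 = 28 patients, or 14 per arm. The documents give no SD. For an assumed SD of 10-20 points, SE = SD × √(2/14) = 3.8-7.6 points. The largest bias, 2.15, is 0.28-0.57 SE and would raise a two-sided 5% type I error to about 6-9%. The smallest, 0.45, leaves it at 5.0-5.2%.

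**5. Would arm sizes show redrawing?** Suppose a supervisor redraws once, in a share q of patients, when the first envelope is not the preferred product, and draws are independent 50:50 picks. The expected count in the preferred arm is 40 × (0.5 + 0.25q). An exact two-sided binomial check (flag at 27 or more, or 13 or fewer; actual size 3.8%) gives:

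| q | Expected count of 40 | Chance of a flag |
|---|---|---|
| 10% | 21 | 4.8% |
| 20% | 22 | 7.8% |
| 30% | 23 | 13.2% |
| 50% | 25 | 31.6% |

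Even with no redraw, independent picks give exactly 20:20 only 12.5% of the time and arms differing by 8 or more 26.8% of the time. An uneven split would therefore prove little. If instead a fixed set of 20 and 20 envelopes is used up over 40 patients, the split is 20:20 whether or not envelopes were swapped along the way. In neither case do the counts stand in for a sequence.

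**The case against.** The strongest reply is that this is a reporting gap. Drawing sealed envelopes without replacement is a valid random mechanism, the contents are hidden until opening, and the faculty are bound to the product named inside. A sound unwritten procedure may exist. All of that is fair.

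Several stronger readings are tempting and are not supported:
- *That the protocol allows envelopes to be put back, redrawn or reused by the operating team.* It permits none of these, and it does not say who picks. The possibility follows only from the absence of a control.
- *That the draw is known to follow sight of the socket, and that envelopes from excluded patients are bound to arise.* The order is left open, and the two statements pull against each other: a later opening makes the second less likely, an earlier one weakens the first.
- *That acknowledged provider preference would put easier sites in one arm.* Section II speaks of cost and handling in routine care, not of choice by socket condition. Redrawing on cost or handling alone would shift arm sizes without a prognostic bias. Socket-guided redrawing is an assumption.
- *That a resulting imbalance could not be found at all.* Crest height, ridge width and buccal plate thickness are measured at extraction and could show part of it, although 40 patients limit what can be seen.

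What remains is that the method as stated is weaker than a readily available alternative. Sealing does not make up for a missing sequence once an envelope is open.

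**Conclusion.** The point holds in a limited form. As described, the allocation method would neither prevent a second draw or the reuse of an excluded patient's envelope, nor make either detectable from an envelope sequence. This says nothing about whether such acts occur. The size of any bias is hypothetical: 0.45-2.15 points of % vital bone under the assumed rates, small beside a standard error of 3.8-7.6 points under the assumed SD, and zero with no redraw. The change is worth making because it is cheap and because a clean sequence is the direct evidence that allocation was followed. It does not show that the trial's comparison is biased.

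**What to change.** Replace the allocation sentence with text to this effect:
- An existing staff member outside the operating team prepares sequentially numbered, opaque, sealed envelopes from a computer-generated 1:1 list and holds the list. Envelopes are used strictly in numerical order.
- Before opening, the study ID, date and time are written on the next-numbered envelope, with a note of whether the socket eligibility check was complete at that time.
- An opened envelope is never returned or reused. Spare numbers beyond 40 are prepared if patients excluded after opening are to be replaced.
- Patients excluded after opening, and any given a product other than the one in the envelope, are logged and reported by arm. Patients are analysed by the product in the envelope.

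The Surgical procedure text should also be reconciled so that the order of socket examination, exclusion for dehiscence and envelope opening is explicit.

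The cost is a few sentences of protocol text, a relabelled set of envelopes with spares, and a short log. Treatment, visits and sample size do not change. The downside is that the list has to be prepared and held away from the surgical team. If envelopes have already been opened, the sponsor can reconcile them against treated and excluded patients and report the method actually used.

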Unpaired Student *t* tests will be used for between-group comparison of ridge dimensions and of percentages of newly formed vital bone, residual bone graft particles, and CT/other. Mann-Whitney U tests will be performed to confirm significant findings based on *t* tests. Discrete measure comparisons for treatments will be performed using Fisher exact tests. For all tests, *P*<0.05 will be considered significant. Pearson correlations will be used to assess the relationships between the histologic bone core percentages for the three tissue groups. Spearman correlations will be used to evaluate relationships between the histologic percentages and the clinical ridge dimension changes in each group.

G. Summarize Knowledge to be Gained:

If there is more vital bone at an earlier time point in Salvin-Oss® than Bio-Oss® then a clinician may re-enter the site at an earlier time point for implant placement.

H. References:

- 4) Van der Weijden F, Dell'Acqua F, Slot DE. Alveolar bone dimensional changes of post-extraction sockets in humans: A systematic review. *J Clin Periodontol* 2009;36:1048-1058.

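### Ridge dimensions are compared by t tests without baseline adjustment, although each baseline is already measured; ANCOVA would be a cheap improvement for these secondary outcomes

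*Combined protocol and SAP*

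**What the plan says.** Section E (Data Analysis Plan) says that unpaired Student t "tests will be used for between-group comparison of ridge dimensions" and of the histologic percentages. It adds that "Mann-Whitney U tests will be performed to confirm significant findings based on" those t tests. No adjusted model or covariate appears in this section or elsewhere.

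The t-test sentence does not itself say which ridge variable is tested, but other text does. Section IV.A and the endpoint list under Study Design and Research Methods name "the change of ridge height on the buccal and lingual", "change of ridge width" and the percentage version of the width change. The Spearman sentence in section E refers to "relationships between the histologic percentages and the clinical ridge dimension changes in each group".

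The surgical procedure text has ridge width and both heights measured at extraction, and the same measurements repeated at implant placement, 16 to 20 weeks later. Section II gives these outcomes secondary status: "The secondary aim is to observe clinical changes in ridge height and ridge width after grafting with these two materials".

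**The concern.** A t test on change subtracts the whole baseline value, that is, it assumes a baseline slope of exactly 1. The slope of follow-up on baseline is rho × k, where rho is the correlation between the two measurements and k is follow-up SD divided by baseline SD. If rho × k is below 1, the change score over-corrects a chance baseline difference between arms; if it is above 1, it under-corrects. ANCOVA estimates the slope from the data.

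In a trial this small, sizeable chance imbalances are not rare. At stake are the width of the confidence intervals for the ridge outcomes and how far each estimate moves with the baseline draw. The baseline values needed for adjustment are already being collected.

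**Working it through.** **Inputs from the documents.** Enrolment (section IV.B): "40 patients, who must be active, non-emergency patients". Allocation (Study Design): "Patients will be randomly assigned (1:1) to one of two treatment groups". Anticipated dropout is 30% (section D) and the significance level is 0.05 (section E), taken as two-sided. The plan gives no power, effect size or SD, so it has no figure of its own to reproduce here.

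**Completers.** 40 × 0.7 = 28, or 14 per arm. This assumes that 40 is gross enrolment and that dropout is even. If 40 is the number completing, it is 20 per arm.

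**Assumed, not in the documents.** rho from 0.5 to 0.9; k of 0.8, 1.0 and 1.2; the same slope and SDs in both arms.

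**Formulas (baseline SD = 1, n per arm).**
- Change-score variance: 1 + k² − 2k·rho, which equals k²(1 − rho²) + (1 − rho·k)²
- ANCOVA residual variance: k²(1 − rho²)
- Penalty for estimating the slope: 1 + 1/(2n − 4), which is 25/24 at n=14 and 37/36 at n=20
- Ratio: k²(1 − rho²) / (1 + k² − 2k·rho) × penalty

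Without the penalty the ratio cannot exceed 1, and it reaches 1 only when rho·k = 1. The penalty is therefore the largest possible loss.

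**Worked cells, n=14.**
- k=1, rho=0.5: 0.75 / 1.00 × 25/24 = 0.781
- k=0.8, rho=0.5: 0.48 / 0.84 × 25/24 = 0.595
- k=1.2, rho=0.8: 0.5184 / 0.52 × 25/24 = 1.038

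**ANCOVA/change variance ratio, n=14.**

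| k | rho 0.5 | rho 0.7 | rho 0.8 | rho 0.9 |
|---|---|---|---|---|
| 0.8 | 0.595 | 0.654 | 0.667 | 0.633 |
| 1.0 | 0.781 | 0.885 | 0.938 | 0.990 |
| 1.2 | 0.907 | 1.007 | 1.038 | 1.018 |

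At n=20 the ratios are slightly lower: 0.771 to 0.976 at k=1, 0.587 to 0.658 at k=0.8, and 0.895 to 1.025 at k=1.2.

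ANCOVA loses only when rho·k is close to 1. At n=14 that means rho above 0.92 at k=1, or rho between about 0.68 and 0.92 at k=1.2. It never loses at k=0.8.

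**Power, n=14.** Suppose the change-score t test has 70% power (noncentrality 2.581, 26 df). With 25 df, ANCOVA then has, for rho 0.5, 0.7, 0.8 and 0.9:
- k=1: 80, 75, 73 and 70%
- k=0.8: 86 to 90%
- k=1.2: 74, 70, 68 and 69%

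**Chance imbalance.** The difference in baseline means has SD √(2/n). At n=14 this is 0.378, so 0.5 SD lies 1.32 standard errors out and the probability of exceeding it in either direction is 0.186. At n=20 it is 0.114.

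**Effect of a 0.5 SD imbalance on the change-score estimate.** The error is 0.5 × (1 − rho·k), in baseline SD units, for rho 0.5, 0.7, 0.8 and 0.9:
- k=1: 0.25, 0.15, 0.10, 0.05
- k=0.8: 0.30, 0.22, 0.18, 0.14
- k=1.2: 0.20, 0.08, 0.02, −0.04 (negative means under-correction)

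**Error rate.** Simulation under no effect at k=1 (20,000 trials per cell, 14 and 20 per arm, rho 0.3 to 0.9) rejected in 0.047 to 0.052 of trials for both analyses.

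**The case against.** The strongest reply is that nothing here is wrong. A change-score t test is valid under randomisation, the ridge outcomes are secondary, and the protocol makes no power claim for them that extra precision would protect. That stands as a limit on the importance of the point. It does not answer the point: adjusting for a baseline already in hand is a recognised gain whose worst case is small and known.

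The second reply is that the gain is unknown for this trial. This also stands. With equal SDs and rho of 0.8 to 0.9 the saving is only about 1 to 6% of variance, and at k=1.2 with rho of 0.7 to 0.9 ANCOVA is marginally worse. The 14 per arm is itself conditional, since section D does not say whether 40 already allows for dropout.

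A reader might infer from the loose t-test sentence that raw follow-up dimensions will be compared, which would discard the baseline entirely and cost far more precision. The documents do not support this. Both outcome lists name changes and no raw follow-up dimension is listed, so the sentence merely lacks a cross-reference.

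A reader might also infer an inflated false-positive rate, because a change-score test rejects too often in badly imbalanced trials. It rejects correspondingly less often in the others, and the overall rate is 5%.

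Finally, an adjusted main analysis and an unadjusted Mann-Whitney check can disagree when the baselines differ by chance. That is a fair criticism of adding ANCOVA without a rule of precedence, so the fix includes one.

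**Conclusion.** The point holds as a cheap improvement, not as an error in the plan. Section E leaves out a baseline adjustment that needs no new data. Over the assumed range at 14 per arm, the effect runs from about 40% less variance (k=0.8, rho 0.5) to about 4% more (the 25/24 cap). With equal SDs it is 1 to 22% less. A baseline imbalance above 0.5 SD would arise in about 19% of trials at 14 per arm, or 11% at 20, and the planned estimate would then generally be shifted.

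These sizes rest on assumed rho and k, equal slopes and SDs in the two arms, and, for the 14, on 40 being gross enrolment with even dropout. The point concerns precision and dependence on chance imbalance in secondary outcomes. It implies neither bias nor a type I error problem, and it does not touch % vital bone.

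**What to change.** Replace the ridge part of the t-test sentence in section E with wording such as:

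> Ridge width, buccal height and lingual height at 16-20 weeks will each be compared between groups by ANCOVA with treatment and the extraction-visit value of the same dimension. The adjusted difference with 95% CI is the main result for that dimension. Mann-Whitney U tests on change from extraction are supportive only, and the ANCOVA result governs if they disagree. % change of ridge width will be reported as listed, with its planned t test.

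The listed change outcomes keep their meaning: with baseline in the model, the adjusted treatment difference is the same whether the outcome is entered as follow-up value or as change.

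Cost: wording in section E, with no new measurements or visits; one degree of freedom per model; and, at worst, about 4% of variance when rho × k is close to 1.
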